A total of 100 PwMCI will be recruited. There will be two treatment arms: N=50 in the MEDSReM-M intervention group, which will be henceforth referred to as MEDManage-S, and N=50 in the standardized educational group, which will be henceforth referred to as the MEDManage-P. This is a multi-site project, and our local (University of Arizona) enrollment goal is n=60 participants. The research team at the University of Illinois Urbana-Champaign aims to enroll n=40 participants.

7.0 Recruitment Methods:

7 1	Salact the	mothods	ot beau	recruit individu	ıəle

⊠ Email	☐ Screening of the Electronic Medical
	Record (EMR)

☑ Face to face	☑ Social media
	☐ SONA System
☑ In person presentations	☑ TV, Radio, Print
☑ Online advertisements	☑ Other – please explain: research
☐ Phone calls	registries

7.2 Explain the recruitment process. Describe how potential subjects will be identified, where recruitment will take place, when recruitment will occur, and the methods that will be used to recruit individuals.

We will use our well-established multi-pronged recruitment strategies, which include word-of-mouth, email, and telephone scripts to members of established registries; flyers and brochures shared by community organizations and partners; advertisements in newspapers and newsletters; potential opportunities on the radio and television and personal visits to community events. All recruitment materials will be pre-approved by the IRB.

- Emails will be used to contact people who have expressed an interest in participating in research studies and are in an existing registry (as in the appendix).
- The same language used in the flyer will be used in flyers (as in the appendix), bookmarks, and brochures. We will work on the graphics to provide these additional means of advertising the study, but the language will not vary from what is shown on the flyer in the appendix.
- If a participant leaves a phone contact, we will call them and share information about the study.
- We will share information about the study at talks given for community centers. We will
 use the encounter forms if people are interested in learning more about the study.
- Social media: using the same language as in the flyer, we will publicize the study on social media, television and print.

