☑ Interviews – virtual/online	☐ Recombinant DNA
☐ Medical records review	☐ Social networking sites
☐ MRI/ultrasound with contrast	☐ Stem cells
☐ MRI/ultrasound without contrast	☐ Radiation Scans (X-Ray, CT Scans, etc.)
☐ Non-invasive instruments (e.g., external sensors applied to the body)	☑ Other activities or interventions – describe: use of a blood pressure device

10.2 Description of research procedures.

To test the MEDSReM-M intervention efficacy, we will conduct a RCT. This is a multi-site study led by MPIs [name] and [name] and includes research staff at the University of Arizona (UofA) and the University of Illinois Urbana-Champaign (UIUC). Throughout the study, research personnel at both UofA and UIUC will adhere to the same study procedures as listed chronologically below:

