The research staff will administer a background questionnaire (Modified TechSAge Background Questionnaire (TBSQ) (REDCap Version for PwMCI) and hypertension knowledge questionnaire (Hypertension Knowledge-Level Scale (HK-LS) ¹. Measures to characterize cognitive abilities and intervention outcomes will be administered, including the: Rey Auditory Verbal Learning Test (RAVLT verbal)²; Benson Complex Figure Copy Test and recall (BCFT) (Visual)³; Trail Making Test (TMT): A &B⁴; Multilingual Naming Test (MINT)⁵; Craft Story 21⁶; Medication Adherence Report Scale (MARS-5)⁷; Mobile Device Proficiency Questionnaire (MDPQ-16)⁸; Delis Kaplan Executive Function System (D-KEFS) Verbal Fluency and Color-Word Interference⁹; National Alzheimer's Coordinating Center (NACC) Number Span Text, ¹⁰; and Prospective and Retrospective Memory questionnaire (PRMQ)¹¹.

Participants will be given a MEMS® medication bottle and cap (AARDEX Group, Liège, Belgium) that will track hypertension medication-taking to establish baseline adherence. Participants will be given a handout on MEMS® medication bottle and cap. If the participant takes more than one hypertension medication, one randomly selected hypertension medication will be monitored via MEMS® cap for 4 weeks for each participant. The names of all hypertension medications will be individually written on a slip of paper of the same size, and all placed in an opaque envelope. One randomly drawn paper will be used to determine the medicine that will be monitored using the MEMS®. The selected medication will be transferred to a MEMS® container by the participant. Participants will be given an adhesive label and asked to write their name, medication name, dosage, and administration instructions from their original hypertension medication bottle. They will be asked to place the completed label onto the MEMS® container. The newly labeled MEMS® bottle will be checked against the original medication bottle label by the research staff to ensure accuracy of the transcribed information. Participants will also be asked to place future refills in the same container. If medicines change, participants will be asked to call the study staff to obtain a new MEMS® cap and container.

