The participant will be asked to record any time in which the participant could not use the container (hospitalizations, vacations, etc., or if they intentionally chose not to take the medication) on a medication log sheet. If a participant is currently using a medication organizer, the organizational strategy will be preserved using a box with seven compartments, each the size of the MEMS® container, for the monitored medication. The seven compartments will be labeled with the days of the week (SMTWTFS), which will allow the participant to move the MEMS® container to the next day after the medication has been taken. If the monitored medication is prescribed more than one time per day, a second box will be provided. In this way, the MEMS® cap can be used for all participants without interfering with their organizational strategies. This ability to maintain the participant's organizational structure was successfully used by the study investigators during previous MPMI and MEDSReM studies.

Visit 1 will be recorded and will take approximately 90-120 minutes. At the completion of the assessment visit, enrolled participants will be compensated (\$30). Research staff will schedule an appointment with participants for Visit 2, four weeks later.

Visit 2 – Intervention (will be audio recorded to ensure fidelity): Visit 2 will involve collecting adherence data and introducing participants to the intervention groups. Adherence data by MEMS® monitoring will be downloaded to a study laptop from all participants' MEMS® caps via a USB connected MEMS® cap reader/communicator. The research staff will review the participant's medication log sheet. The research staff will take both standing and seated BP. If elevated BP (>180 mm Hg systolic or >110 mm Hg diastolic) or unusually low BP reading (<90 systolic) or BP drops more than 20 mmHg between sitting and standing measurements, the research staff will encourage participants to contact their primary care provider. After these measures are obtained, staff will determine the participant's group assignment (MEDManage-S or MEDManage-P) based on randomization.

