If the participant is eligible for the study, they will receive information on hypertension and medications. Participants may also improve their medication taking.

12.0 Risks to Subjects:

12.1 Describe all physical, psychological, social, legal, and/or economic risks that could be associated with participation in this research.

The primary risks of the evaluations and observations are fatigue and frustration due to the difficulty of some tasks. We will provide encouragement, scheduled breaks, and a supportive environment to make participation an interesting and beneficial experience.

There is a risk related to inadvertent loss of confidentiality of one's health-related information. Potential participants will be informed of the risks inherent in participating in this project and of the procedures to minimize any of these risks from occurring. The topic of the proposed research is not deemed to be particularly sensitive or emotionally charged. MEDSReM-M does not change the participants' medications. Although this study includes a technology designed to improve medication adherence and standardized educational intervention for the comparison group, we do not anticipate any health risks resulting from participation in the MEDSReM-M intervention or Standardized Education control group.

For participants who currently use a pillbox or organizer the use of the medication bottle with the special cap may interfere with their existing strategies to remind them to take their medications. To mitigate this interference, those who use a pillbox or organizer will be supplied a box that allows them to move the MEMS® container from one day to the next. All participants in the MEDSReM-M intervention will be provided with a pillbox and encouraged to use it. The box will be labeled with the day of the week, consistent with pill organizers.

12.2 Discuss what steps will be taken to minimize risks to subjects/data.

We will provide encouragement, scheduled breaks, and a supportive environment to make participation an interesting and beneficial experience and minimize fatigue during assessments.

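### Section 12.1 gives the MEDSReM-M arm an encouraged pillbox that the arm definition and Visit 2 omit, so the protocol does not fix whether the app or the app plus a pillbox is tested

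*Protocol*

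**What the plan says.** Section 12.1, in a paragraph on interference between the MEMS bottle and people's own pill organizers, states: "All participants in the MEDSReM-M intervention will be provided with a pillbox and encouraged to use it". The next sentence says the box carries day-of-week labels. Nothing equivalent is stated for controls.

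The same paragraph also says that "those who use a pillbox or organizer will be supplied a box that allows them to move the MEMS® container" from day to day. Section 10.2, Visit 1, has the matching provision: "If a participant is currently using a medication organizer, the organizational strategy will be preserved using a box with seven compartments". Visit 1 precedes randomization, so this provision applies to both future arms.

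The arms are defined in 10.2 under Randomization Process. MEDManage-S gets the app and standardized education through the portal. MEDManage-P gets the education and portal without the app. The Visit 2 text covers installing the app, opening the portal and, for both arms, a blood pressure monitor. It lists no pillbox. Section 10.2 opens by saying that personnel at both sites "will adhere to the same study procedures as listed chronologically below". Section 11.1 describes the system as app and portal. At Visit 4, staff collect the MEMS cap and a pillbox, with no arm named.

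**The concern.** Both arms receive the education and the portal, so as defined in 10.2 the randomized contrast is the app. A day-labelled box is itself a way to remember a dose and check that it was taken. Section 12.1 treats organizers as part of how people remind themselves, and section 1.0 calls the ability to check intake a critical component of the strategies behind the system. An encouraged pillbox in one arm therefore plausibly acts on adherence, a trial outcome, and by a mechanism the app also claims.

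At stake is what the trial can conclude. With two components given to the same arm and not listed together anywhere, a positive result could be reported for the app and portal when part of it may come from the pillbox. There is also a fidelity problem. Section 10.2 has sessions checked for drift from the intervention protocol, but issuing this pillbox follows 12.1 while the listed Visit 2 steps do not include it. Two sites could resolve that differently.

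**Working it through.** The protocol gives no figure on this point to reproduce. The check is a comparison of its sections, followed by one count.

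1. **Whom the 12.1 sentence covers.** Section 6.3 fixes the term: "N=50 in the MEDSReM-M intervention group, which will be henceforth referred to as MEDManage-S". The paragraph of 12.1 just before the pillbox paragraph sets the same term against the other arm: "participation in the MEDSReM-M intervention or Standardized Education control group". The natural reading is one arm of 50.

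2. **Whether the arm's content includes it.** The MEDManage-S definition (10.2), the Visit 2 steps (10.2) and the description of the system (11.1) do not.

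3. **Whether the Visit 1 box is the same provision.** Its scope differs. Visit 1 describes a box for current organizer users in either arm, and 12.1 adds a pillbox for everyone in one arm. The objects may be the same, since both are day-labelled, but the protocol does not say so.

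4. **When it could start.** Visit 2 is where staff determine the "group assignment (MEDManage-S or MEDManage-P) based on randomization". A pillbox that depends on the arm cannot be issued before that. No issue date is given. If it is issued at Visit 2, it runs beside the app for 4 weeks to Visit 3 and 8 weeks to Visit 4: 4 + 8 = 12 weeks, all of the follow-up after assignment.

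5. **What it holds.** At Visit 1, "The selected medication will be transferred to a MEMS® container by the participant". The protocol does not say whether the 12.1 pillbox carries that container. If it instead held the monitored tablets, cap openings would no longer track doses, and in one arm only.

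6. **How many participants differ in provision.** Let p be the share already using an organizer at Visit 1, taken as equal in both arms. The protocol does not give p. Followed as written, and with no wider provision to controls, 50 of 50 intervention participants have a box and 50 × p controls do. Controls without one number 50 × (1 − p):
   - p = 0.3: 50 × 0.7 = 35
   - p = 0.5: 50 × 0.5 = 25
   - p = 0.7: 50 × 0.3 = 15
   - limits: 50 at p = 0, and 0 at p = 1

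   The values of p are assumptions. Even at p = 1 the arms still differ, because encouragement is stated for one arm only.

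7. **Size of effect.** Step 6 counts boxes, not adherence. The protocol gives neither uptake of the pillbox nor its effect beyond an app that already lets users check their intake. No contribution to the arm difference can be calculated.

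**The case against.** The strongest reply is that the sentence may be meant for the whole study. The protocol sometimes uses MEDSReM-M as a study label (the research team office in 9.3, the safety monitoring schedule in 15.3), 10.2 once calls the two arms both intervention arms, and the paragraph concerns MEMS interference, which affects everyone. Visit 4 collects a pillbox without naming an arm. This lowers confidence but does not overturn the arm reading, which rests on section 6.3 and on the adjacent paragraph of 12.1.

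A reader might go further and infer that the protocol restricts boxes to organizer users, so that any wider provision contradicts it. It does not: neither Visit 1 nor 12.1 says only. On a study-wide reading there would be no arm difference, and what remained would be an unclear sentence. A reader might also infer that staff who follow 10.2 issue no pillbox at all. That is too firm, because Visit 4 presupposes that some pillbox was issued, possibly the Visit 1 box.

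It is also fair to say that the stated aim compares a system with standardized education and promises no attribution to components. That stands, and it makes this a question of what the package is, not of validity. But 11.1 describes the system as app and portal, so a conclusion worded that way would not match arms that also differ by a pillbox.

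**Conclusion.** The concern holds and should be fixed, with medium confidence. Section 12.1 and the arm definition disagree about what MEDManage-S participants receive. If 12.1 is followed, the randomized comparison is valid for the app plus an encouraged pillbox, on top of portal education. It does not isolate the app, and a difference in MEMS adherence or blood pressure cannot be credited to the app and portal alone.

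This rests on the arm-specific reading of 12.1 and on no other passage giving the same pillbox and encouragement to controls; none was found. A reader might infer that the comparison is biased by some stated amount. The protocol does not support that: randomization still protects the package comparison, and organizer use at baseline, pillbox uptake and pillbox effect are all unknown.

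**What to change.** Reconcile 12.1 with 10.2 in one of two ways. The protocol gives no ground for ranking one above the other, since the pillbox may be an intended part of the intervention.

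- **Same provision in both arms.** State one box provision, with the same encouragement and timing, for MEDManage-S and MEDManage-P. The contrast is then the app. The cost is a change in what one arm is offered, or extra boxes for controls without an organizer: 15 to 35 across the assumed shares in the working, and 50 at most.
- **Pillbox as a named component.** Add it to the MEDManage-S definition and to the Visit 2 steps, and state the conclusion as app plus pillbox on top of portal education. This costs only wording, but gives up attribution to the app alone.

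In either case, state who receives the pillbox, at which visit, whether it holds the MEMS container, and from whom it is collected at Visit 4. Record organizer use at Visit 1, so that the number newly given a box in each arm is known.

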We are contracting with Ephibian, a local computer science and electrical engineering company. Ephibian serves as a technical resource to the research team linked to the MEDSReM-M system and will not directly interact with participants. Ephibian builds high-performance software solutions and for more than 25 years has served multiple audiences including the aging population; in particular, the Patient Reported Outcomes Consortia (http://c-path.org/programs/pro/). Ephibian helped develop the first version of MEDSReM and the advanced design of our MEDSReM-M system. They specifically built the system to protect the smartphone's local device information with encryption, protect all data transmissions, require pin entry for application access for additional user security, remove any data on user request or application uninstallation, and meet HIPAA security requirements.

6.0 Study Population:

6.1 Select all the categories of participants included in the research:

☐ Healthy adults	☐ Non-English-speaking subjects
⊠ Non-healthy adults	☐ UA staff/faculty
☐ Children (under 18 years old) *	☐ UA students
☐ Pregnant women, neonates, and/or fetuses*	☐ Banner employees
☐ Prisoners*	☐ Refugees
☐ Native Americans, Alaskan Native, and Indigenous Populations*	☑ Other – please explain: PwMCI have only mild problems with cognition. They can make
☐ Adults unable to consent (i.e., cognitively impaired adults) *	independent decisions without needing assistance and are capable of providing informed consent.

6.2 For each of the above selected categories, describe the inclusion and exclusion criteria. Indicate age range, gender, and ethnicity.

PwMCI will meet the following general inclusion criteria: i) 60 years or older, ii) community-dwelling, iii) fluent in English, iv) have adequate self-reported visual and hearing ability to interact with others and with the smartphone, v) self-reported memory problems, (vi) the Modified Telephone Interview for Cognitive Status (TICS-M)¹ score between 27-37, vii) self-managing at least one antihypertension medication, viii) no diagnosis of dementia or other neurological disorders such as stroke, traumatic brain injury (TBI), and Parkinson's disease, ix) no major history of depression or other mental health diagnoses, and x) use a smartphone. Participants who do not meet these general inclusion criteria will be excluded.

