Phone Screening: Phone screening will not be recorded. Formal recruitment will be completed via phone to ensure privacy and individual attention. The research staff will follow up with interested potential participants who have shared their telephone contact information, ideally the next day for recruitment into the study. The team will document all attempts to contact potential participants and will vary the day and time of contact attempts if the person is not reachable on the first attempt. During the screening call, verbal consent will first be obtained prior to asking questions to determine eligibility. The research staff will confirm that participants meet the following criteria: i) 60 years or older, ii) community-dwelling (that is not in an assisted living situation) iii) able to speak and read English, iv) have adequate self-reported visual and hearing ability to interact with others and the smartphone, v) self-reported memory problems, vi) managing at least one hypertension medication, vii) no self-reported diagnosis of dementia or other neurological disorder such as stroke, TBI, and Parkinson's disease, viii) no major history of depression or other mental health diagnoses, and ix) experience using a smartphone. If participants are eligible, they will complete the Modified Telephone Interview for Cognitive Status (TICS-m); eligible participants will score between 27-37. The research staff will clearly explain the time commitment, expectations for participation, and answer any questions the participant asks. If the person expresses interest in enrolling and is eligible, the participant will be scheduled for a video screening. The phone screening will span approximately 5-15 minutes.

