Video Screening: After providing electronic informed consent, participants will complete video screening. The video screening will be recorded. Video screening will include the Montreal Cognitive Assessment (MoCA), and Geriatric Depression Scale (GDS). Participants will also complete questionnaires on demographic information (age, gender, education, race/ethnicity, income, living situation, comorbidities, and medications), nature of support received by a caregiver, and health status. Responses to these items can be entered by the data collector directly into an electronic file. Participants with MoCA cut-off scores between 20 to 26 will be invited to participate in the study and complete an in-person baseline assessment. If they agree to participate, they will be scheduled for in-person consent for the RCT and baseline assessment. If a participant does not qualify or prefers not to participate despite being eligible, they will be thanked for their participation. The video session will last approximately 45 minutes. All participants regardless of eligibility will be paid \$15 for the video screening session.

Visit 1 Baseline Assessment: The baseline assessment will be scheduled within three months of the video screening. Informed consent will be completed in-person for the RCT in a private space by research staff who are trained in Human Subjects Protection before study procedures are administered. Upper arm circumference will be measured to determine the appropriate-sized blood pressure monitor cuff. To obtain blood pressure readings (BP), the research staff will use the Omron 3 Series Upper Arm Blood Pressure Monitor (FDA approval: https://fda.report/PMN/K062027), if participants require an XL BP cuff. Utilizing the 2017 American College of Cardiology/American Heart Association's guidelines for home blood pressure measurement (HBPM), BP readings will be obtained both standing and sitting. If a problem is detected

during the visit, for example an elevated BP (>180 mm Hg systolic or 110 mm Hg diastolic), or an unusually low BP reading (<90 systolic), or BP that drops more than 20 mmHg when standing, the research staff will encourage participants to contact their primary care provider.

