14.8 For EACH of the storage locations checked above, discuss the type of data to be stored, including if the data is identifiable, coded, or de-identified upon storage, and who may have access to the data.

We will be using computer-based data collection procedures for assessment via REDCap. Information about this research study will remain confidential. All participants will be assigned a participant code that is not related to their personal information in any way. This participant code will be used for all inperson data collection. There will be one master sheet linking participant names and device usernames to the participant code. This sheet will be electronically stored on Box with restricted access to the research team. Any electronic copies of the data including audio files will be stored by participant code that only the research team has access to, including the interview recordings. Once recording files are uploaded to Box, these files will be deleted from the initial recording device. Strict security will be maintained to access Box. No identifying information will be mentioned in any presentations or publications.

Ephibian, our contracted MEDSReM (iOS app and portal) developer, uses Microsoft's Azure cloud services platform to host and support the necessary MEDSReM servers and corresponding operating systems and software. MEDSReM's required servers include database, web, and Application Programming Interface (API) servers. Azure supports HIPAA compliance and incorporates all the necessary safeguards to ensure HIPAA requirements can be satisfied. Microsoft provides a secure VPN and web portal to connect to Azure, so any data uploaded to or downloaded from Azure is encrypted and all data stored in its cloud instances are encrypted. HIPAA requires access controls to be implemented to limit who can access Box. Azure offers these controls and uses Active Directory to allow permissions to be set. Azure includes detailed logging, so administrators can see who accessed, or attempted to access Box.

The MEMS® cap records and stores the date and time when the participant opens the study bottle. During the study visits a MEMS® USB NFC (Near Field Communication) reader will be used to transfer the time-stamped medication taking events from the MEMS® cap to a password protected laptop only accessed by study staff. These data will be uploaded and stored in Box.

14.9	Storage of research records (research records should be maintained for whichever of

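### The written smartphone criterion does not ensure that a person randomized to MEDManage-S can install the study app: the only platform named is iOS, any smartphone user is eligible, and installation comes after assignment.

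*Protocol*

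**What the plan says.** **Platform.** Section 14.8, which answers where study data are stored, refers to "our contracted MEDSReM (iOS app and portal) developer". No other operating system is named for the app anywhere in the protocol. Section 5.0 says that the same contractor "helped develop the first version of MEDSReM and the advanced design of our MEDSReM-M system".

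**Eligibility.** The last inclusion item in section 6.2 reads "and x) use a smartphone". The matching item in the phone screen (10.2) reads "and ix) experience using a smartphone". Neither mentions platform or compatibility with the app.

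**Steps between screening and assignment.** The video screening in 10.2 lists the MoCA, the GDS, "demographic information (age, gender, education, race/ethnicity, income, living situation, comorbidities, and medications", and items on caregiver support and health status. Visit 1 adds a background questionnaire, cognitive tests and a device measure that, by its title, concerns proficiency. None of these is described as a check that the app can be installed.

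**Order of events.** Under 10.2, staff determine the assignment at Visit 2, after the adherence download and the blood pressure readings. Staff then help MEDManage-S participants put the app on their own phones. MEDManage-P participants are shown how to reach the education portal on theirs. Section 15.2 says that data from people who withdraw are kept because the analysis is by intention to treat.

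**The concern.** The app is the main difference between the arms: both receive portal-based education, and only MEDManage-S receives the app. Whether a phone can take the app is settled before randomization, but the written procedure meets the question only afterwards, and in one arm only. Once someone has been assigned to MEDManage-S, they cannot be removed for having an unsuitable phone without departing from intention to treat.

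If such people are enrolled, those assigned to MEDManage-S get close to the control condition and are analysed as treated. The difference in adherence and in SBP shrinks, in a trial with 50 per arm. The adoption aim in section 3.0 is exposed under the same condition, because a phone that cannot run the app could be counted as a person who did not adopt it.

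**Working it through.** The protocol states no figure on this point, so the check is a reading of the passages in the order in which a participant meets them.

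1. **Who is let in.** Under 6.2 a person must use a smartphone; under the phone screen, have experience of using one. Section 6.2 excludes anyone who fails its list, so its item applies to all. A user of any make of smartphone passes both.
2. **What is checked before assignment.** The listed contents of the phone screen, video screening and Visit 1 include no step that would stop a person whose phone cannot take the app.
3. **How long the gap is.** "The baseline assessment will be scheduled within three months of the video screening", and then "Research staff will schedule an appointment with participants for Visit 2, four weeks later". Up to 3 months plus 4 weeks, about 4 months, can pass between video screening and assignment. A phone could be replaced in that time, so a single early check would not settle the matter.
4. **When installation is attempted.** At Visit 2, after assignment, in MEDManage-S only, on the participant's own phone. No loan phone is mentioned, and nothing is said about what happens if installation fails.
5. **What the app runs on.** Section 14.8 names iOS under the product name MEDSReM. Section 1.0 distinguishes MEDSReM from the refined MEDSReM-M. Section 14.11, however, uses both names for the system that supplies this study's data, and section 5.0 gives both the same developer. If 14.8 describes the trial app, the only platform stated is iOS. If it describes the other product, the trial app's platform is stated nowhere. Either way, the protocol does not establish that the app runs on every phone that 6.2 admits.
6. **Direction of the effect.** Let p be the share of MEDManage-S participants who cannot install the app, and r the fraction of the full effect that they still obtain. The intention-to-treat contrast is then 1 − p(1 − r) times the full contrast. It equals the full contrast when p = 0 and falls as p rises, for any r below 1. Because these participants still get the portal (10.2) and a pillbox (12.1), r may be above zero.
7. **Size.** The protocol gives neither p nor r. It also gives no effect size, standard deviation, significance level or power. Any percentage loss or loss of power would therefore be built wholly on assumed inputs, and none is offered here.

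**The case against.** The strongest reply is that everything turns on one parenthesis in an answer about data hosting. It uses the name MEDSReM and does not say iOS-only, while section 5.0 describes the security of the trial system on smartphones without any platform limit. A reader might infer that the app is confined to iOS and that users of other phones will be randomized to something they cannot use. The protocol does not support that: other platforms are unmentioned, not ruled out. The harm is conditional, and this part of the objection stands.

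A reader might also infer from the phone-screen wording that someone with no phone could be enrolled. That is weak. Section 6.2 still requires current use, section 9.2 requires the general inclusion criteria again before consent to the trial, and 10.2 takes it for granted that participants in both arms have phones. The two wordings should agree, but the difference is not evidence of a looser gate.

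Nor can it be said that phone type goes unrecorded. The screening and background questionnaires are not shown and may ask about it. Recording the device would still not make it a condition of entry, and the entry rule in 6.2 is visible.

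Finally, non-receipt of the app under intention to treat weakens the contrast. It neither breaks randomization nor favours the intervention. That is correct, and it limits the seriousness of the point.

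**Conclusion.** The concern holds as a conditional one. As written, the criteria and the order of assignment and installation do not prevent the randomization to MEDManage-S of people whose phones cannot take the app. This becomes a real loss only if MEDSReM-M does not run on every common platform, which the protocol leaves open. In that case the adherence and SBP contrast is pulled toward zero by an amount that the protocol gives no basis to quantify; if every enrolled phone is compatible, there is no loss.

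This is more than a missing detail, because the remedy changes a stated eligibility rule and has to act before randomization. Confidence is moderate, since the platform evidence is a single phrase and the screening forms are not available.

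**What to change.** - In 14.8, state which platforms MEDSReM-M supports, using that name.
- Give the smartphone item in 6.2 and in the 10.2 phone screen the same wording, for example: uses their own smartphone on which the MEDSReM-M app can be installed.
- Confirm this for every participant, in both arms, before the assignment is opened at Visit 2.

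The cost is one sentence in 14.8, one aligned eligibility item and a short check before assignment. If the app is limited to one platform, the recruitment pool shrinks and the results apply only to users of supported phones; that restriction should then be stated. If all common platforms are supported, the change costs almost nothing in recruitment.
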